[name] [name] [name] [name]	FISABIO GSK GSK GSK	Medical Doctor Epidemiologist Medical expert Statistician	Supervision and medical consultant Supervision and advice Supervision and advice Supervision and advice

1. Rationale and background

COVID-19 is an infectious disease caused by the severe acute respiratory syndrome coronavirus 2 (SARS-CoV-2) first identified in Wuhan, China, in December 2019 (1). As of March 10th, 2021, COVID-19 pandemic has resulted in more than 117 million confirmed cases and above 2.6 million deaths worldwide (2). Therefore, SARS-CoV-2 outbreak has led to the largest and more severe pandemic since the influenza pandemic in 1918-19 (3). Spain ranks as the seventh most affected country with more than 3 million cases and 71,727 deaths (2). To date, the Spanish region Community of Valencia has registered 381,919 positive cases and 6,911 deaths (4).

SARS-CoV-2 infection may be asymptomatic or cause a wide spectrum of symptoms that may appear after a variable period of incubation (average time from exposure to onset is 5 days; 97.5% of people who develop symptoms do so within 11.5 days) (5). Among them, the most common symptoms derive from the primary infection of the respiratory tract and consist of dry cough, shortness of breath and fever (5). Additional symptoms include fatigue and changes to taste and smell (5, 6). However, SARS-CoV-2 infection has also been associated with alterations in the CNS and peripheral nervous system (7), liver (8), cardiovascular system (9), kidneys (10) and skin (11, 12).

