4.4 Sars-Cov-2 exposure

Exposure status of everyone might change within the follow up period (Figure 3): Sars-Cov-2 unexposed in the pre-pandemic period and Sars-Cov-2 exposed in the pandemic period. Sars-Cov-2 exposure levels will be treated as a time-varying variable and the following states will be considered:

- 1) **Sars-Cov-2 unexposed**: subject's follow up period from the start of follow-up to the declaration of the pandemic in Spain (March 14th 2020).
- 2) **Sars-Cov-2 exposed**: subject's follow up period from the start of the pandemic. We will consider the following 2 comparison groups:
 - **Sars-Cov-2 free**: time from the start of pandemic (or the follow-up) to the date of the first Sars-Cov-2 confirmation (by PCR or Ag test). If no Sars-Cov-2 positive test registered, the time period will be until the end of follow-up.
 - **Sars-Cov-2 laboratory-confirmed**: time from the date of the SARS-CoV-2 positive result in RedMiva to the end of follow up.

[figure not shown]

Figure 3. Example of exposure, follow-up and comparisons in the study.

* Subjects with recurrent episodes of Sars-Cov-2 will be treated separately. If the sample size is not large enough for the analysis, these individuals will be excluded for the analysis.

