4.6.3 Comorbidities

Comorbidities that have been identified as risk indicators for HZ will be considered for the analysis. These conditions will be identified by systematic search of ICD-codes in the hospital or ambulatory databases, MBDS or SIA. Subjects will be considered to

Disease classification	ICD-10
Diabetes	E10-E14
COPD	J44
Ischemic heart disease	120-125
Other heart disease	127-152
Kidney disease	N18-N19
Immunocompromised	
HIV	B20-B24
Cancer	C00-D49
TOTS	Z94
IBD	K50-K51
RA	M05-M14
SLE	M32

have a given condition from the first appearance of the comorbidity-related diagnosis date until the end of the follow-up period.

COPD: chronic obstructive pulmonary disease, HIV: human immunodeficiency virus, TOTS: Transplanted organ and tissue status, IBD: inflammatory bowel disease, RA: rheumatoid arthritis, SLE: systemic lupus erythematous.

Presence of any comorbidity.

This is a binary variable indicating whether the patient has at least one comorbidity defined above.

Number of underlying conditions

This is a categorical variable indicating the number of comorbidities (0, 1, 2, 3+).

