4.9.6 Primary objective

To develop the primary objective, we will compare the incidence of HZ among SARS-Cov-2 free and Sars-Cov-2 laboratory-confirmed subjects 50 years and older during the pandemic period. For this purpose, models using individual patient data or grouped will be implemented.

[figure not shown]

Figure 4: Cohort diagram for HZ rates comparison among subjects with and without previous episode of COVID19

The risk of HZ in subjects with Sars-cov-2 respect to subjects without Sars-Cov-2 will be estimated by a multivariate Poisson or negative binomial model according to applicability assumptions. Individual data will be grouped by SARS-Cov-2 free and Sars-Cov-2 laboratory-confirmed exposure, age, sex and comorbidities. Individual and grouped data can both be analyzed with the Poisson (or Negative binomial) distribution. Given the usual large size of the cohort, estimation when using grouped data is considerably quicker than when using individual level data and the results for both approaches are remarkably similar.

The number of HZ cases by aggregation unit will be compared among SARS-Cov-2 free and labconfirmed subjects. Age, sex, and comorbidities will be considered for the adjustment, and the person-time-at-risk (in years) as an offset term. RR and their 95% confidence or credible intervals will be reported.

Besides, individual-level risk of HZ between SARS-Cov-2 free vs lab-confirmed will be estimated by Cox regression model for right censored data. The abovementioned variables will be also considered for the adjustment.

Both approaches will be performed and compared for the robustness of the results.

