4.9.8 HZ incidence rates (Descriptive analysis)

[figure not shown]
Incidence rates (number of patients with an incident case of HZ per 1000 persons-years) will be obtained for subjects with and without Sars-Cov-2 in the pandemic period by sex, age-group and comorbidity. HZ incident rates for the pre-pandemic period will be also described by sex, age-group and comorbidity.

The person-time-at-risk (in days) ends at the date of the first event of HZ or the end of follow-up, whichever comes first. Follow-up time will be split according to the time-varying covariates (calendar year, month, week, age and comorbidities). Persons-years will be calculated as the sum of total person-time-at-risk divided by 365.25. Rates 95% confidence intervals will be calculated by the Exact Poisson method.

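### Comorbidity status keeps updating after the positive test and is adjusted for in the primary models, which may attenuate the RR; confirmed time should use pre-test comorbidities only

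*Protocol*

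**What the plan says.** Four parts of the protocol combine.

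- Section 4.6.3 selects the covariates for their link with the outcome: "Comorbidities that have been identified as risk indicators for HZ will be considered for the analysis". They are "identified by systematic search of ICD-codes in the hospital or ambulatory databases, MBDS or SIA", and each counts "from the first appearance of the comorbidity-related diagnosis date until the end of the follow-up period". Nothing stops or lags this at the positive test.
- Section 4.4 defines laboratory-confirmed time as "time from the date of the SARS-CoV-2 positive result in RedMiva to the end of follow up".
- Section 4.9.6 states for the Poisson or negative binomial model: "Age, sex, and comorbidities will be considered for the adjustment". For the Cox model it adds: "The abovementioned variables will be also considered for the adjustment".
- Section 4.9.8 treats comorbidity as changing over time: "Follow-up time will be split according to the time-varying covariates (calendar year, month, week, age and comorbidities)".

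Section 4.9.9 analyses adults aged 18 and over in the same way. It also adjusts the 1-, 3- and 6-month logistic models for these covariates without saying at what date comorbidity status is read. The limitations in section 4.10 do not mention the issue.

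**The concern.** The primary objective compares HZ risk with and without confirmed infection, which reads as a total effect. Updating a confounder up to exposure is sound. Updating it afterwards conditions on something exposure may have changed. There are two routes.

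1. **Mediation.** Section 1 associates infection with alterations of the "cardiovascular system (9), kidneys (10) and skin (11, 12)", and section 4.6.3 lists heart and kidney disease among the HZ risk indicators. HZ risk that runs through such disease would be adjusted away.
2. **Detection.** Comorbidities are read from hospital and ambulatory records, and Annex 1 requests up to 30 discharge diagnoses per admission. An admission for COVID-19 can bring older, uncoded disease into the record. A free subject has no equivalent occasion. Recording then differs between the groups being compared, and the confirmed group's unrecorded stratum becomes healthier than the free group's.

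At stake is the size of the primary RR in a study planned around RR 1.1 with a stated power of 0.76.

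**Working it through.** **1. The plan's own figure.** Inputs from section 4.9.5: free rate λ0 = 0.007 per person-year, RR 1.1 (λ1 = 0.0077), N1 = 110,000 confirmed, N0 = 2,000,000 free, level 0.05. One person-year per person is implied. Two-sided Poisson Wald test with pooled variance under the null:

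- pooled rate = (847 + 14,000)/2,110,000 = 0.0070365
- null SE = √[0.0070365 × (1/110,000 + 1/2,000,000)] = 0.0002598
- alternative SE = √[0.0077/110,000 + 0.007/2,000,000] = 0.0002711
- power = Φ[(0.0007 − 1.96 × 0.0002598)/0.0002711] = Φ(0.704) = 0.759

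The plan states 0.760864, so its figure reproduces.

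**2. Detection route.** Assumptions, not in the documents: true RR 1.10; true comorbidity prevalence 45% or 50% in confirmed and 40% in free; comorbidity-HZ rate ratio 1.3 or 1.5; no false codes; 80% of true comorbidity recorded in the free group. Group sizes and the 7 per 1000 rate are from section 4.9.5. The summary is the Mantel-Haenszel rate ratio over recorded strata: Σ(cases₁ × PY₀/PY) ÷ Σ(cases₀ × PY₁/PY).

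Worked cell (45%, rate ratio 1.5, recording 95% against 80%). The rate without comorbidity is 7/(0.6 + 0.4 × 1.5) = 5.833 per 1000.

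| Stratum | Confirmed PY | Confirmed cases | Free PY | Free cases | Stratum RR |
|---|---|---|---|---|---|
| Recorded | 47,025 | 452.6 | 640,000 | 5,600 | 1.100 |
| Not recorded | 62,975 | 412.0 | 1,360,000 | 8,400 | 1.059 |

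- Numerator: 452.6 × 640,000/687,025 + 412.0 × 1,360,000/1,422,975 = 421.6 + 393.8 = 815.4
- Denominator: 5,600 × 47,025/687,025 + 8,400 × 62,975/1,422,975 = 383.3 + 371.7 = 755.0
- Adjusted RR = 1.080

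The whole loss arises in the unrecorded stratum. Across the assumed prevalences and rate ratios:

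| Recorded, confirmed / free | Confirmed subjects without a code who gain one | Adjusted RR (truth 1.10) |
|---|---|---|
| 80% / 80% | none | 1.104–1.113 |
| 85% / 80% | 3.5–4.2% | 1.098–1.103 |
| 90% / 80% | 7.0–8.3% | 1.089–1.096 |
| 95% / 80% | 10.5–12.5% | 1.080–1.089 |

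The middle column is p × (s − 0.80)/(1 − 0.80p), with p the prevalence and s the recording in confirmed. Perfect recording in both groups returns 1.100.

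**3. New codes after the test.** A Poisson regression on expected counts, with exposure, comorbidity and a log person-time offset, was scaled to give RR 1.10 when status is frozen at the test. Assumption: 40% comorbid at the test in both groups. Status was then updated:

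- rate ratio 1.3, new codes in 1% of previously uncoded confirmed against 0% of free: 1.098
- 1.5, 5% against 1%: 1.089
- 3, 10% against 2%: 1.045

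The updated RR was the lower one in each scenario. That sign depends on new codes accruing faster in confirmed time.

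**4. Time available.** From the section 4.9.4 monthly counts and mid-month dates, 288,311 positive results carry on average about 2.6 months to 31 December 2020. October to December contributes 200,596 of them (70%). Section 4.2 allows a later end date.

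**5. Power.** The step 1 formula gives about 0.66 at RR 1.089 and 0.58 at 1.080, against 0.76 at 1.10, all with the plan's one person-year per person.

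**The case against.** The strongest reply is that the bias may be negligible and that freezing has its own bias. Much of this stands.

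- No passage gives a post-test coding rate. The 95% row needs more than a tenth of uncoded confirmed subjects to gain a first listed code, applied as if from the first day of confirmed time. At 85% the updated rule is essentially unbiased.
- Pre-test status is not free of error either. Some codes dated after the test are older disease, and so true confounders. The 80%/80% row shows the residual confounding this leaves: 1.104 to 1.113. On these assumptions the updated rule is nearer the truth at 85%, and the two errors are of similar size at 90%.
- Mediation is thin for much of the list. HIV, transplant status, IBD and SLE are unlikely to arise from infection within months, and average follow-up is short. Codes entered at the COVID-19 admission itself would still count.
- The sentence on splitting follow-up is in the descriptive section, and section 4.9.6 says only that comorbidities will be considered. Model detail may be in an analysis plan not shown. Still, section 4.6.3 gives a general definition and the protocol offers no other.

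A reader might infer that the primary RR is certainly biased downward, by about a fifth of the planned effect. The documents do not support this: a fifth is only the far end of the 95% row. A reader might also infer that status should be fixed for everyone at 14 March 2020. That would discard legitimate confounders first recorded between that date and infection.

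**Conclusion.** The concern holds as a matter of analysis choice. The protocol's stated comorbidity rule adjusts confirmed time for status that infection or its care can change, in both primary models. Attenuation of the RR is the expected direction, on two conditions: the listed conditions raise HZ risk, as the protocol presumes, and they are coded faster after a positive test than in free time, which it does not quantify. Under the assumptions of step 2, the result runs from no material bias at 85% recording to a loss of 0.011 to 0.020 at 95%, that is, a tenth to a fifth of the 10% effect. The figure of 1.045 in step 3 needs a comorbidity-HZ rate ratio of 3 and new codes in 10% of confirmed subjects, and nothing in the documents supports either. The change is worth making because it is cheap and the planned power leaves little room, not because a large bias has been shown.

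**What to change.** In section 4.6.3, and by reference in sections 4.9.6 and 4.9.9:

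- Keep time-updated comorbidities up to the positive test, and throughout SARS-CoV-2 free time.
- For laboratory-confirmed time in the primary and 18-and-over models, use only comorbidities recorded before the positive test date.
- Use the same pre-test status in the severity and 1/3/6-month models, which currently have no stated date for it.
- Report the fully time-updated version as a sensitivity analysis. A clear gap between the two would show that post-test coding matters.

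The cost is one changed covariate derivation, using diagnosis and test dates that Annex 1 already requests. The statistical downside is that older disease first coded after the test goes unadjusted, leaving slight residual confounding (upward by 0.004 to 0.013 in the 80%/80% illustration). The limitations in section 4.10 should say so.

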4.6.4 Temporal variables

Temporal variables such as calendar week, month and year will be contemplated to detect trends.

4.7 Data sources

4.7.1 The Valencia healthcare Integrated Databases (VID) - Real World Data

The Valencia Region accounts with the Valencia Health System Integrated Database (VID) [27], one of the best clinical and administrative databases to perform observational studies using RWD. VID is a set of multiple, public, population-wide electronic databases including sociodemographic and administrative data, clinical (hospital and GP setting), vaccination registry and microbiology databases (including both positive and negative results). Importantly, VID allows linking all these databases at individual level using the personal ID number of each citizen of The Region.

[figure not shown]

Figure1: Scheme of the Valencia Health System Integrated Database (VID); VIS, Vaccine Information System; RedMIVA, Microbiological Surveillance System; CIS, Cancer Information System; SIER-CV, Rare Diseases Information System; CAR, Congenital Abnormalities Registry; BIMCV, Medical Image Bank; CRC, Catalogue of Corporate Resources; MBDS, Minimum Basic hospital Data Set; AED, Accident & Emergency Department record; GAIA, Pharmaceutical Module; SIA, Ambulatory Information System

The following registries from VID will be used for the study:

Population-based administrative database (SIP)

The regional population-based administrative database, SIP (Personal Information System), collects and updates demographic data, health services assignment, and access to public health services for both residents of the Valencia Community and non-residents with access to public health services. It includes APSIG characteristic which is an identification code defined for each person at any time including: inhabitant's registration status, nationality (Spanish or not), sex, year of birth, health department assigned, health care insurance, residence status, migrations, work activity, geopolitical group, and social exclusion. Since 2005, SIP can be linked with the hospital discharge database. All other healthcare databases are able to capture the demographic data from SIP.

Primary Care Database

Abucasis SIA-GAIA (Ambulatory Information System - Care provision management) is a primary care database used across the entire Valencia healthcare system that contains medical information for each patient attended in the Primary Care (PC) setting (General Practitioners, GPs, and specialists). It was set up in 2006 and the percentage of the population included increased from 73.1% in 2007 to 88.8% in 2008 and to 95.7% in 2009. This database contains primary care diagnoses (physician coded using the International Classification of Diseases Revision, Clinical Modification (ICD-CM)) and all drug prescriptions (using Anatomical Therapeutic Chemical (ATC) Classification System). In addition, the physician or paediatrician and nurse responsible recorded text about each episode and about the patient is included. The database is also used at Specialty Centres and is considered reliable since 2007.

Hospital Discharge Database

The Spanish hospital discharge database, MBDS (Minimum Basic Data Set), collects diagnosis and procedures as an assessment of medical activity. The coding system used is ICD-9-CM until 2016 and ICD-10-CM afterwards. The main discharge diagnosis is coded in first position, and diagnosis relevance decreases as the position number increases. Using MBDS is compulsory for all public hospitals, and over 95% of all discharges are included. According to the Spanish Ministry of Health, data are considered reliable since 2002.

Microbiological Surveillance Network

The Microbiological Surveillance Network (RedMIVA) contains all the results (positive or negative) given by all the microbiology laboratories of the Valencian Public System network. All data is transferred from the laboratories to the RedMIVA database on a daily basis. Data are considered reliable since 2008.

4.8 Data collection

The following variables (Annex 1) will be requested to the different databases for the period from July 2017 until at least December 31st 2020 (depending on the date of data extraction) for subject's \geq 18 years. Data privacy will be protected by using dissociated data.

4.9 Sample size considerations

4.9.1 Cohort estimations

[figure not shown]
Currently, approximately 4,900,000 inhabitants of Valencia Region are covered by the PHS. Since the study is restricted to subjects aged 18 years and older and approximately 20% of the Spanish population is younger than 20 years (data from Statistics National Institute, INE), we might expect approx. 4 million subjects to fulfil the inclusion criteria.

4.9.2 HZ incidence rates estimations

Data from a previous study from our team (28), using the same health databases from Valencia Region showed an incidence rate of HZ of 5.02 (4.99–5.04), 5.3 (5.3-5.4), 7.3 (7.2-7.4), 8.3 (8.2-8.4) and 8.6 (8.5-8.8) per 1000 persons-year in subjects \geq 18, 50-59, 60-69, 70-79 and \geq 80 years old, respectively.

4.9.4 Number of tests performed in The Region over time

As of December 31st 2020, a total of 2.112.504 SARS-CoV-2 tests were performed. The following table shows the monthly number of positive and negative tests (both PCR and Ag) performed.

			Negative	results		Positive results					
Month	Total tests	Total negatives	% of total	AG	PCR	Total	% of total	AG	PCR		
feb-20	514	468	91,05058366		468	46	9,829059829		46		
mar-20	39403	26394	66,98474735		26394	13009	49,28771691		13009		
abr-20	80998	69783	86,15397911		69783	11215	16,07124944		11215		
may-20	114973	112264	97,64379463		112264	2709	2,413062068		2709		
jun-20	101371	100395	99,03719999		100395	976	0,972159968		976		
jul-20	133709	128809	96,33532522		128809	4900	3,804082013		4900		
ago-20	243498	216819	89,04344184		216819	26679	12,30473344		26679		
sept-20	269026	240845	89,52480429	912	239933	28181	11,74536225	109	28072		
oct-20	305193	255984	83,87610463	11170	244814	49209	20,10056614	4832	44377		
nov-20	394144	323865	82,16920719	44718	279147	70279	25,17634078	14560	55719		
dic-20	429675	348567	81,12340723	67192	281375	81108	28,82558863	20070	61038		
Total 2020	2112504	182/103	86 35216785	123002	1700201	288311	16 957/6562	30571	2/87/0		

4.9.5 Power Calculation for HZ IR comparison among SARS-Cov-2 labconfirmed and SARS-Cov-2 free.

Considering an HZ IR of 7 cases per 1000 persons-year in SARS-Cov-2 free, and the following expected populations: 110 000 SARS-Cov-2 lab-confirmed and 2 000 000 SARS-Cov-2 free, we would be able to find statistically significant (significance level = 0.05) differences in RR for HZ (SARS-Cov-2 free vs. Lab-confirmed) of 10% (RR 1.1) with a power of ~ 80% (power = 0.760864).

Power calculation was estimated based on the Two-sample Poisson Ratio Tests (Different Sizes) from the PASSED package of R (version 4.0.2).

Statistical analysis

4.9.6 Primary objective

To develop the primary objective, we will compare the incidence of HZ among SARS-Cov-2 free and Sars-Cov-2 laboratory-confirmed subjects 50 years and older during the pandemic period. For this purpose, models using individual patient data or grouped will be implemented.

[figure not shown]

Figure 4: Cohort diagram for HZ rates comparison among subjects with and without previous episode of COVID19

The risk of HZ in subjects with Sars-cov-2 respect to subjects without Sars-Cov-2 will be estimated by a multivariate Poisson or negative binomial model according to applicability assumptions. Individual data will be grouped by SARS-Cov-2 free and Sars-Cov-2 laboratory-confirmed exposure, age, sex and comorbidities. Individual and grouped data can both be analyzed with the Poisson (or Negative binomial) distribution. Given the usual large size of the cohort, estimation when using grouped data is considerably quicker than when using individual level data and the results for both approaches are remarkably similar.

The number of HZ cases by aggregation unit will be compared among SARS-Cov-2 free and labconfirmed subjects. Age, sex, and comorbidities will be considered for the adjustment, and the person-time-at-risk (in years) as an offset term. RR and their 95% confidence or credible intervals will be reported.

Besides, individual-level risk of HZ between SARS-Cov-2 free vs lab-confirmed will be estimated by Cox regression model for right censored data. The abovementioned variables will be also considered for the adjustment.

Both approaches will be performed and compared for the robustness of the results.

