4.5 Other health outcomes

4.5.1 Pandemic and pre-pandemic periods

- Pre-pandemic period will be considered from January 1st 2018 to March 14th 2020
- Pandemic period will be considered from March 14th 2020 to the end of study period

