4.6 Covariates

Covariate information will be collected on sociodemographic, spatial information, vaccination against Sars-Cov-2 and comorbidities. The source of the eHR databases and the variables needed to create the covariates is given in Annex 1.

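### The primary Poisson/negative binomial model leaves out calendar time although SARS-CoV-2 exposure is tied to calendar date, so any common drift in recorded HZ during the pandemic enters the RR

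*Protocol*

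**What the plan says.** Protocol 4.9.6 sets the primary comparison: "we will compare the incidence of HZ among SARS-Cov-2 free and Sars-Cov-2 laboratory-confirmed subjects 50 years and older during the pandemic period". Section 4.5.1 fixes the window: "Pandemic period will be considered from March 14th 2020 to the end of study period". For the Poisson or negative binomial model, 4.9.6 gives the cells, "Individual data will be grouped by SARS-Cov-2 free and Sars-Cov-2 laboratory-confirmed exposure, age, sex and comorbidities", and the covariates, "Age, sex, and comorbidities will be considered for the adjustment, and the person-time-at-risk (in years) as an offset term".

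A second, individual-level analysis is "estimated by Cox regression model for right censored data". Its covariates are the same: "The abovementioned variables will be also considered for the adjustment". No time scale is given. The two approaches are to be compared for robustness.

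Under 4.4, exposure is time-varying. Free time runs from the start of the pandemic, or of follow-up, to the first positive test; lab-confirmed time runs from the positive result onward.

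Calendar time appears in two other places. Section 4.6.4, under Covariates, says: "Temporal variables such as calendar week, month and year will be contemplated to detect trends". Section 4.9.8, on descriptive rates, splits follow-up by calendar year, month and week. Neither is carried into the model of 4.9.6.

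**The concern.** Nobody can contribute lab-confirmed time before a positive test, and most positives in the protocol's own table come late in 2020. Lab-confirmed time is therefore late time, while free time is spread evenly from mid-March. Once the data are collapsed over exposure, age, sex and comorbidity, the month is lost. If recorded HZ changed during the pandemic for reasons common to both groups, such as consultation behaviour, coding or season, the model attributes part of that change to SARS-CoV-2.

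The primary RR is at stake. The target effect is small (RR 1.1), so a modest calendar drift matters, and its sign is not known in advance. A larger cohort would narrow the interval around the biased value without removing the bias.

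**Working it through.** **Benchmark effect.** Section 4.9.5 assumes 7 HZ cases per 1000 person-years in free subjects, 110,000 lab-confirmed and 2,000,000 free subjects, alpha 0.05 and RR 1.1, and reports power 0.760864. Taking one person-year per subject and a two-sided Wald test on log RR:

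- SE = √(1/(110,000 × 0.0077) + 1/(2,000,000 × 0.007)) = √(1/847 + 1/14,000) = 0.0354
- Power = Φ(0.0953/0.0354 − 1.96) = 0.768

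A pooled-variance test gives 0.759. The stated figure is reproduced, so RR 1.1 is the yardstick.

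**Person-time by calendar month.** Inputs:

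- Monthly positives, March to December 2020 (4.9.4): 13,009; 11,215; 2,709; 976; 4,900; 26,679; 28,181; 49,209; 70,279; 81,108 (288,311 with February).
- These are scaled to the 119,935 confirmed cases aged over 50 (4.9.3), in a population of 110,000 + 2,000,000 = 2.11 million.
- Cases are spread evenly within each month (March cases over 14-31 March), with follow-up from 14 March to 31 December 2020. Deaths and other exits are ignored.

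| Period | Lab-confirmed PY | Share | Free PY | Share |
|---|---|---|---|---|
| 14 Mar-May | 1,673 | 6.3% | 454,700 | 27.3% |
| Oct-Dec | 18,587 | 70.4% | 512,884 | 30.8% |
| Whole period | 26,412 | 100% | 1,666,210 | 100% |

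**RR under no true effect.** Let h be the relative level of recorded HZ in each month, the same in both groups. A model without month returns

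RR = Σ(lab-confirmed share × h) / Σ(free share × h).

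For a dip d confined to March-May this is (1 − 0.0633d)/(1 − 0.2729d):

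- d = 20%: 0.9873/0.9454 = 1.04
- d = 30%: 0.9810/0.9181 = 1.07
- d = 50%: 0.9683/0.8636 = 1.12

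On the log scale these are about 45%, 70% and 120% of log 1.1. A spurious 1.10 needs d = 0.1/(1.1 × 0.2729 − 0.0633) = 42%.

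**Sensitivity.**

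- Dip lasting March-June (shares 9.9% and 37.6%): 20/30/50% give 1.06/1.09/1.17, and 1.10 needs a 32% dip.
- June-September excess of 10% or 20%: 0.98 or 0.97, the opposite direction.
- Follow-up to 30 June 2021, no cases added after 2020 and no vaccine censoring (March-May shares 1.9% and 17.1%): March-May dips of 20/30/50% give 1.03/1.05/1.08.

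The dips and excesses are assumptions. With month in the model, the RR is 1.00 in every scenario by construction, because h is the same for both groups within a month.

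**Cox model.** With time-varying exposure and a common origin or calendar clock, each case is compared with people at risk on the same date, so h cancels. If the clock instead restarts at the positive test, day 30 for a November case (in December) is set against day 30 for a free subject (13 April), and h does not cancel. Section 4.9.6 does not say which applies.

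**The case against.** - **The Cox model may already be protected.** A reader might infer that Poisson and Cox share the bias and would agree with each other. The documents do not support that. Section 4.4 makes exposure time-varying, and the start rule in 4.2 gives most people aged 50 and over a common origin. On that reading the Cox estimate is free of this confounding, and a disagreement with Poisson would expose it. This stands, except that the clock is unstated and the Poisson estimate stays biased.
- **The size is not established.** A reader might infer that the bias equals the 10% target effect. The documents contain no monthly HZ rates, and only the more extreme assumed dips reach 1.10. The studies cited in the background report more HZ after pandemic onset, not less. This stands: the imbalance can be approximated from the protocol's own table, but the bias itself is conditional.
- **Later extraction dilutes it.** The end date is at least 31 December 2020, and the timeline marks extraction in July 2021, October 2021 and January 2022. The bias shrinks but remains. Vaccination also ends follow-up, with an effect that cannot be sized here.
- **The inputs are proxies.** The table counts all-age tests (288,311), whereas 4.9.3 gives 219,144 cases. No monthly curve of first positives at 50 and over is shown. The exact shares are therefore approximate.
- **Model detail belongs in the SAP.** For the Cox clock, that is fair. For the Poisson model, the protocol itself fixes the cells and covariates without calendar time.

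Section 4.6 also states: "Covariate information will be collected on sociodemographic, spatial information". A reader might infer that omitting social and spatial variables confounds the RR too. The documents give no evidence that infection clusters by place or social group, or that these variables affect recorded HZ, so that does not form part of this point.

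**Conclusion.** The point holds for the Poisson/negative binomial model as written: calendar time is an uncontrolled potential confounder of the primary RR. The imbalance is large, at roughly 70% against 31% of person-time in October-December and 6% against 27% in 14 March-May, on all-age tests as proxy and a 31 December 2020 cut-off.

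The resulting bias depends on how recorded HZ moved, which the documents do not show. Over the assumed March-May dips of 20% to 50% it runs from RR 1.04 to 1.12, or 1.03 to 1.08 with follow-up to June 2021. That is a material part of the target effect and reaches it only at the extreme; a summer excess would push the RR below 1. For the Cox model the conclusion is narrower: its protection depends on a time scale that 4.9.6 leaves open. The model should be corrected before analysis.

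**What to change.** In 4.9.6, add calendar month to the grouping cells and as a factor in the Poisson/negative binomial model, using the split already planned in 4.9.8. For the Cox model, state calendar time as the time scale, with delayed entry and the time-varying exposure of 4.4.

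The cost is wording and more cells: a 31 December 2020 cut-off spans ten calendar months, so up to ten times as many. No new data are needed. The precision loss should be slight, because free person-time greatly exceeds lab-confirmed person-time even in December (170,337/8,746 ≈ 19 to 1).
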